6.2.3.3 Analytical Methods

Plasma samples will be analyzed to determine concentrations of DYN101 using a validated, specific and sensitive method.

DYN101 metabolites in plasma and urine will be identified and profiled in an exploratory manner.

A validated ELISA method will be used to determine the presence and level of anti-DYN101 antibodies in plasma.

6.2.3.4 PK Parameters

The PK parameters of DYN101 will be derived using non-compartmental analysis methods with the plasma concentration-time data from all evaluable subjects. Actual sampling times, rather than scheduled sampling times, will be used in all computations involving sampling times. The following PK parameters will be calculated for plasma concentration values of DYN101.

Parameter	Definition
AUC_{τ}	Area under the plasma concentration-time curve during a dosing interval
AUC_{last}	Area under the plasma concentration-time curve from time 0 to time of the last quantifiable concentration
AUC_{∞}	Area under the plasma concentration-time curve from time 0 to infinity
$R_{ac(AUC)}$	Accumulation ratio based on AUC_{τ}
$R_{ac(C_{max})}$	Accumulation ratio based on C_{max}
C_{max}	Maximum plasma concentration
$C_{av, SS}$	Average plasma concentration during a dosing interval at steady state
CL	Clearance after IV administration
λ_z	Terminal disposition phase rate constant
$t_{1/2}$	Terminal disposition phase half-life
t_{max}	Time of first occurrence of C_{max}
V_z	Apparent volume of distribution during the terminal disposition phase

The effects of ADA on the PK parameters will be assessed.

6.2.4 Pharmacodynamic/Exploratory Efficacy Evaluations

The following PD/exploratory efficacy evaluations will be performed at specified time points as indicated in the [TRIAL SCHEDULES](#). The questionnaires should be completed first, then the other assessments will be performed in the order listed:

- 1) QoL and health outcome questionnaires
- 2) EAT-10 Dysphagia questionnaire
- 3) Respiratory function tests
- 4) Muscle Strength and Function Tests:
 - a. MyoGrip
 - b. MFM32

All assessments, including their collection, management, and reporting, are described in detail in a separate Site Operations Manual.

6.2.4.1 Quality of Life and Health Outcome Questionnaires

The following questionnaires will be assessed:

- Patient Reported Outcomes Measurement Information System (PROMIS®) is a National Institutes of Health Initiative, created to assess patient-reported health status for physical, mental, and social well-being to reliably and validly measure patient-reported outcomes in chronic diseases for clinical research and practice. The PROMIS domains tested in this trial are Anxiety, Depression, Fatigue, Pain Interference, Ability to Participate, and Physical Function.
- Clinical Global Impression of Improvement (CGI-I) is a 7-point scale ranging from (1) very much improved to (7) very much worse and is used to assess global changes in the subject's condition compared to the condition before treatment. Wherever possible, the same clinician must complete the CGI-scale during the trial for the same subject. Results will be documented in the source documents.
- Patient Global Impression of Change (PGI-C) is a scale similar to the CGI-I. It is a 7-point scale ranging from (1) very much improved to (7) very much worse and needs to be completed independent of the investigator who completes the CGI-I, so neither party knows how the other has rated the scale. The subject (assisted by site personnel if needed) will complete PGI-C scale in the subject's source documents.
- Goal Attainment Scaling is an instrument that is intended for individual evaluation of an intervention. It allows subjects to set individual goals, together with their physician. The number of goals and the content of these goals may differ per subject, but the attainment of the goals is measured in a standardized way. This makes a standardized evaluation of an intervention possible, even when the subjects are all in a different stage of their disease. The physician selects objectives for each affected domain (respiratory, muscle strength and function, dysphagia) together with the subject, and records this in the eCRF. At the final assessment, the goal is evaluated on a 3-point scale by the physician and the subject.

6.2.4.2 Dysphagia Questionnaire

Dysphagia is a relatively frequent problem in patients with CNM, particularly in those with XLCNM, and increases the risk of aspiration pneumonia, requiring the use of gastrostomy feedings. The Eating Assessment Tool (EAT-10) questionnaire will be used to assess swallowing difficulties and will be completed by the subject.

6.2.4.3 Respiratory Function Tests

Assessment of the respiratory function will be performed with a handheld device, by qualified site personnel. To prevent air leaks, the nose will be blocked by a nose clip for every respiratory assessment.

For each parameter, the attempt should be repeated at least 3 times making sure that the subject has recovered between attempts. If, at each attempt, there is an improvement in the results, further tests can be conducted until the subject has achieved his/her best result.

The following measurements will be performed:

- **Forced Vital Capacity (FVC):** the maximum amount of air that a person can exhale as hard and as long as possible from the lungs after a maximum inspiration.
- **Forced Expiratory Volume (FEV1) in the first second of exhalation:** FEV1 is the most frequently used index for assessing airway obstruction, bronchoconstriction or bronchodilatation. The ratio of FEV1 and FVC is the standard index (also called Tiffeneau index) for assessing and quantifying airflow limitation.
- **Maximum Expiratory and Inspiratory Pressures (MEP and MIP):** these measurements assess the overall respiratory muscle strength. MIP reflects the strength of the inspiratory muscles, while MEP reflects the strength of the abdominal muscles and other expiratory muscles. This examination can detect early respiratory muscle weakness before the onset of a decrease in vital capacity.

Measurements will be expressed as percent of predictive value.

In addition, ventilation requirements will be recorded in the eCRF.

6.2.4.4 Muscle Strength and Function Tests

All muscular testing will be done by a certified physiotherapist.

The measurements will take place in a quiet and acclimatized room. All tests will be performed with the subject sitting in a regular chair or in their wheelchair facing a table, preferably adjustable in height with the forearm placed on the table or on the wheelchair shelf. Before each test, subjects will be given a description of the task, a demonstration of the expected movement and advice on the correct practice. If necessary, the correct body position will be manually guided. If standard upper limb position described in the assessment protocol (which will be provided to the sites) cannot be maintained because of contractures, an alternative position will be allowed.

The subjects will perform the strength tests first (MyoGrip), followed by the functional tests (MFM32). To limit fatigue, only the subject's dominant side will be tested, i.e. the hand preferred for fine motor skills such as writing. Each strength test must be repeated at least 3 times or repeated until the last attempt is less successful than the previous one. The retained value will be the maximal reproducible strength and should be within 10% of another attempt. Subjects will be given a 3-minute rest between each test.

Functional tests will be video-recorded after signed consent to constitute a visual record of the subject's ability. The subject or his/her representative have the right to refuse the video recording or request filming of only a specific frame (e.g. only the hand), a specific time period, or anonymization of the recording. In case the video will be used outside of the study team involved in the trial as a visual representation of the effect, the subject will be asked for a separate consent.

- **MyoGrip** is an extremely sensitive tool to measure muscle strength in severely disabled subjects where current tools are unable to measure changes or benefit (Servais et al., 2013). For disorders such as CNM, the ability to use the joystick of their electric wheelchair or other fine motor functions is important to the subject. These sensitive measures can also assist in detecting early signals of efficacy of an administered drug (Seferian et al., 2015).
- **Motor Function Measure (MFM)** is classically used as a measure of functional capacities in subjects with neuromuscular disorders (Bérard et al., 2005). The MFM 32-item list (MFM32) is a scale to enable an objective assessment of the motor abilities of subjects with neuromuscular diseases whatever the motor function deficiency. Three dimensions are taken into account: D1: standing position and transfers, D2: axial and proximal motor function, and D3: distal motor function.

6.2.5 Collection of Optional Samples for Exploratory Research (Blood Biomarkers)

Samples will be taken and stored from subjects who signed a separate ICF for further exploratory research (refer to Section 10.4.4). Blood-based biomarkers allow to explore how biomarker/genetic variations may affect the clinical parameters associated with the response to DYN101 and potentially the basis of CNM.

If the subject is very light weight, anemic, or presenting with symptoms of fatigue, main study samples are to be taken first, exploratory samples may to be skipped due to the subject's status.

A blood sample for DNA will be taken only once at SAD baseline (or at MAD baseline for replacement subjects who did not participate in SAD) and blood samples for biomarkers will be taken at the time points defined in the [TRIAL SCHEDULES](#).

6.2.6 Muscle Biopsy

Muscle biopsies will be performed at the time points defined in the [TRIAL SCHEDULES](#). Details will be described in the Site Operations Manual.

Muscle ultrasound imaging of both the vastus lateralis and biceps brachii will be performed at screening to determine which muscle should be biopsied. This imaging should not be older than 6 months at baseline, otherwise it should be repeated. Muscle biopsies should be obtained from the vastus lateralis according to the site's standard practice (open or needle biopsy) if sufficient muscle mass is identified after ultrasound imaging and muscle depth and location allow. In the event inadequate muscle tissue is identified in the vastus lateralis after ultrasound imaging, or it is determined that the location of a suitable vastus lateralis muscle is not easily accessible, a biopsy should be obtained from the biceps brachii (open or needle biopsy). For subjects undergoing an open muscle biopsy, general anesthesia can be applied. There should be 24 hours between the muscle biopsy and the IMP administration.

Platelet counts need to be verified before a muscle biopsy is performed (the samples for verification of the platelet counts cannot be older than 3 days). The muscle biopsy should be the last assessment at the visit. Platelet counts will need to be verified again before IMP administration (local assessment) only if the previous platelet count is more than 3 days old.

The level of *DNM2* mRNA as well as the concentration of DYN101 will be measured. This evaluation will allow for a measure of target engagement (i.e. the amount of decrease of *DNM2*) and will support the start of the MAD3 cohort and a dose selection for further clinical trials based on the PK/PD modelling, in addition to preclinical data, and results of some of the exploratory efficacy assessments.

In addition, a section of the muscle will be prepared for histology.

In case sufficient muscle biopsy material is left, the material will be stored for further exploratory research (see Section 10.4.4).

6.2.7 Volume of Blood to be Drawn from Each Subject

All blood samples will be collected via an indwelling catheter. The volume of blood to be drawn from each subject is presented in Table 4.

Table 4: Volume of Blood to be Drawn from Each Subject

Assessment	Sample Volume (mL)	Number of Samples ^{a)}	Total Volume (mL)
Safety samples – clinical laboratory tests			
Biochemistry (8.5 mL)	8.5	16	136.0
Biochemistry (5.0 mL)	5.0	19	95.0
Bile Acids	3.5	35	122.5
Complement	5.0	1	5.0
Hematology	2.0	31	62.0
Coagulation - local	4.5	31	139.5
Platelet count – local	1.0	31	31.0
Cardiac troponin	2.5	14	35.0
Erythrocyte sedimentation rate - local	2.0	30	60.0
PK samples ^{b)}			
PK evaluations	4.0	33	132.0
Anti-drug antibodies	4.0	5	20.0
Metabolic profiling	4.0	2	8.0
Blood biomarkers samples (optional)	9.0	6	54.0
DNA sample (optional)	2.5	1	2.5
Total Volume of Blood (mL)	57.5		902.5

a) Not including any additional samples taken after MAD Week 25.

b) If a catheter is used, the first 1 mL is to be discarded and 3 mL is taken into an appropriate tube for PK samples. Therefore, a total of 4 mL is indicated as the sample volume.

Note: The above volume of blood to be taken for each assessment is an estimate. The volume of blood to be taken may vary according to the instructions provided by the manufacturer or laboratory for an individual assessment. The estimated total blood volume does not include blood draws during unscheduled visits. When more than 1 blood assessment is to be done at the same time point/period, if they require the same type of tube, the assessments may be combined.

The total blood volume to be collected is considered to be within the limits of standard blood donation.

6.2.8 Sample Management

Samples will be labeled with the protocol number, the subject's trial identification number and information related to the sample. No personal identifiers (e.g. date of birth, subject initials) will be recorded on the sample labels. Leftover samples may be used in the future for additional exploratory research.

Sample collection and processing will be performed by qualified site personnel according to current versions of approved standard operating procedures. The Laboratory Manual contains further details regarding the collection, handling, labeling, and shipment of biological samples to the respective laboratories.

7. SAFETY DEFINITIONS, REPORTING AND FOLLOW-UP

7.1 Adverse Event Definitions

An AE, an adverse drug reaction (ADR), and an SAE are defined according to the International Council for Harmonisation of Technical Requirements for Pharmaceuticals for Human Use (ICH) Guideline E2A.

An AE is any untoward medical occurrence in a subject administered the IMP and which does not necessarily have a causal relationship with this IMP or the IMP administration procedure. An AE can therefore be any unfavorable and unintended sign (including an abnormal laboratory finding), symptom, or disease temporally associated with the use of the IMP including the IMP administration procedure. The definition also covers medication errors and uses outside what is foreseen in the protocol, including misuse and abuse of the product.

An ADR is an untoward and unintended response to the IMP related to any dose administered. A causal relationship between the IMP and the AE is at least a reasonable possibility.

An SAE is any untoward medical occurrence that at any dose:

- Results in death
- Is life-threatening (this refers to an event in which the subject was at risk of death at the time of the event; it does not refer to an event that hypothetically might have caused death if it was more severe)
- Requires in-subject hospitalization or prolongation of existing hospitalization
 - The hospitalization of a subject who decides to stay in the hospital overnight in advance or following IMP administration, for convenience based on personal choice or at the recommendation of the investigator without the presence of an AE warranting such hospitalization, is not considered an SAE.
- Results in persistent or significant disability or incapacity
- Is a congenital anomaly or birth defect

- Is judged medically important by the investigator (this refers to an event, not resulting in any of the outcomes listed above, but may jeopardize the subject or may require intervention to prevent one of the other outcomes listed)

A suspected unexpected serious adverse reaction (SUSAR) is any suspected adverse reaction that is both serious and unexpected.

The IB should be referenced for events that are considered expected.

In the following situations events are not defined as an AE:

- Medical or surgical procedure (e.g. endoscopy, appendectomy); the condition that leads to the procedure is an AE.
- Anticipated day-to-day fluctuations of pre-existing disease(s) or condition(s) present or detected at the start of the trial that do not worsen.
- Condition(s) for which pre-planned procedure(s) have been recorded at screening, including hospitalization(s), unless the condition(s) for which the procedure and/or hospitalization was planned has worsened from the first trial-related activity after the subject has signed the main ICF.
- Concomitant illness identified during the screening procedures will be recorded as medical history. However, whenever symptoms for these condition(s) worsen and/or become serious, then these events must be reported as an AE or SAE, as applicable.

7.2 Adverse Events of Special Interest

The events described in this section will be reported as AEs, will be marked as AEs of special interest in the eCRF, and reported within 24 hours of the investigator becoming aware of the AE of special interest.

Thrombocytopenia, impaired hepatic or kidney function are AEs of special interest, as they have been described with the use of ASOs previously, both in the preclinical and the clinical setting. Therefore, subjects experiencing reduced platelet counts or showing signs of impaired hepatic or kidney function, as evident by laboratory testing (see Section 7.11.2) should be examined by a physician as soon as possible and retested.

Vasculitis is an AE of special interest as vasculitis which appeared to be associated with chronic complement activation with subsequent depletion and inflammation was observed in a 9-month preclinical study with DYN101 in NHP. Therefore, subjects with any suspicion for vasculitis (vasculitis of any origin, including the complement pathway) will trigger a consult with an appropriate specialist for further investigation.

Although there is no clinical experience with DYN101 yet, some ASOs have been associated with an increased risk for thrombocytopenia. All subjects enrolled in clinical studies with DYN101 must be informed of the potential risk of severe thrombocytopenia.

The investigator will diligently monitor each subject's platelet count and must be in receipt of an interpretable platelet result before a scheduled IMP administration on the time points indicated in the [TRIAL SCHEDULES](#). Investigators should ensure that subjects are queried about the possibility of spontaneous bleeding at routine study visits.

Subjects must also be instructed to urgently notify their doctor if they develop any symptoms consistent with thrombocytopenia or abnormal bleeding. It is recommended that subjects should be provided with an information leaflet describing these alert symptoms. These symptoms are as follows:

- Nosebleed, bleeding from gums (either spontaneously or on brushing teeth), dark or bloody stools or blood in urine, vomiting blood, unusually heavy menstrual bleeding (period), or other unusual bleeding (for example prolonged bleeding after a cut or abrasion);
- More frequent or easy bruising or bruising without injury;
- Pinpoint-size red or purple spots on the skin, in the lining of the mouth, or the white of the eye;
- Neck stiffness, unusual drowsiness, worsening headache, blurred or double vision;
- Worsening abdominal pain.

As there are no validated specific diagnostic markers to detect vasculitis, monitoring and assessment should be based on a high level of clinical awareness/suspicion and on physical examination and objective studies specific to the end organs that could be involved in drug-induced small or medium vessel vasculitis. These include, but are not limited to, the heart, kidney, lungs, liver, peripheral nervous system, and skin. In order to monitor for potential cases of vasculitis the following aspects need to be taken into account:

- The physical examination performed by the investigator should include head, eyes, ears, nose, throat, heart, lungs, abdomen, extremities, examination of the skin for purpura, as well as neurological assessments for any new onset of paresthesia or dysesthesia.
- Laboratory parameters, including cardiac troponin, complete blood count, clinical chemistry, liver and kidney function tests, urinalysis, and acute phase reactants like CRP and ESR have to be reviewed with the awareness of potential signals of end organs and non-specific markers of inflammation.

In case of suspicion of vasculitis, refer to the Site Operations Manual for guidance on further work-up and consults with appropriate specialists.

The investigator should also consider whether alternative explanations for the finding may be likely (e.g. recent antibiotic use when the subject presents with a rash) and how characteristic the finding is of vasculitis (e.g. a non-specific skin rash should be further investigated, but a purpuric rash should raise a higher level of suspicion, as it is more suggestive of vasculitis).

7.3 Clinical Laboratory Abnormalities and Other Abnormal Assessments as Adverse Events or Serious Adverse Events

Laboratory abnormalities without clinical significance based on the investigator's judgment, are not considered AEs or SAEs. However, laboratory abnormalities (e.g. clinical chemistry, hematology) or other abnormal (clinical trial-specific) assessments (e.g. ECG, vital signs) that require medical or surgical intervention, are associated with signs and/or symptoms, lead to IMP

interruption, modification, or discontinuation must be reported as an AE or SAE if they meet the definitions as described in Section 7.1. If the laboratory abnormality is part of a syndrome, the syndrome or diagnosis is to be reported (e.g. anemia instead of decreased hemoglobin).

If a laboratory abnormality meets the criteria of a pausing stopping rule, appropriate action should be taken, as explained in Section 7.11.

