3.3 Trial Endpoints

3.3.1 Primary Endpoint

- Comparison of adverse event (AE, SAE, AESI) frequency and severity by dose (cohort), for single or multiple administration, and by mutated gene (sub-cohort) and overall using the Safety Analysis Set following 12 weeks of MAD treatment and after 24 weeks of MAD treatment (12 weeks in the MAD part + 12 weeks in the MAD extension part; Week 25 visit) or discontinued earlier.

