7.4 Overdose

An overdose is defined as a known deliberate or accidental administration of IMP to or by a subject, at a dose greater than 110% of the dosage assigned to that individual subject according to the trial protocol.

All cases of overdose (with or without associated AEs) will be documented in the eCRF. Cases of overdose without manifested signs or symptoms are not considered AEs. AEs associated with an overdose will be documented in the eCRF.

SAEs associated with overdose should be reported according to the procedure outlined in Section 7.7.

In the event of overdose, the subject should be treated symptomatically.

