### **6.14.1 Adverse Events**

Adverse events will be reported separately for SAD and MAD + MAD Extension parts.

A pre-therapy AE is defined as any AE that starts before the first dose of study drug.

A treatment emergent adverse event (TEAE) is defined as:

- Any AE that has an onset on or after the first dose of study drug and before last dose of study drug + 28 days.
- Any pre-existing AE that has worsened in severity on or after the first dose of study drug and before the last dose of study drug + 28 days.

A treatment-related AE is defined as an AE as being related to the study drug. If an AE has missing relationship it is assumed to be related to the study drug for analysis purposes.

Maximum severity will be assumed for an AE with missing severity.

The following tables will be presented for AEs:

- Summary of All Adverse Events, incidence and the number of events.
- Pre-therapy AEs by system organ class and preferred term, incidence and number of events
- TEAEs by system organ class and preferred term, incidence and number of events
- Treatment-related TEAEs by system organ class and preferred term, incidence and number of events

- Serious TEAEs by system organ class and preferred term, incidence and number of events
- TEAEs leading to treatment withdrawal by system organ class and preferred term, incidence and number of events
- All AEs of special interest by system organ class and preferred term, incidence and number of events
- TEAEs by system organ class, preferred term and maximum severity, incidence
- Treatment related TEAEs by system organ class, preferred term and maximum severity, incidence
- TEAEs by system organ class, preferred term and study drug relationship, incidence
- Listing of Deaths (presented in the Table section of the appendices)
- Listing of Serious TEAEs (presented in the Table section of the appendices)

All AEs will be listed.

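### With no laboratory cut-off for AESIs, an asymptomatic platelet fall becomes reportable through the dose hold in MAD but only by judgement in SAD, so the primary AESI comparison is not like for like for platelets

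*Protocol*

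**What the plan says.** The primary endpoint (protocol 3.3.1) is a "Comparison of adverse event (AE, SAE, AESI) frequency and severity by dose (cohort), for single or multiple administration", and by mutated gene. SAP 6.14.1 tabulates AEs separately for SAD and for MAD plus extension, and includes a table of "All AEs of special interest by system organ class and preferred term, incidence and number of events".

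Four rules decide what enters that table.

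- **Protocol 7.2** names thrombocytopenia, impaired hepatic or kidney function, and vasculitis as AESIs. It says: "The events described in this section will be reported as AEs, will be marked as AEs of special interest in the eCRF". It gives no numeric cut-off. For subjects with "reduced platelet counts or showing signs of impaired hepatic or kidney function, as evident by laboratory testing (see Section 7.11.2") it asks for prompt examination by a physician and a retest.
- **Protocol 7.3, exclusion:** "Laboratory abnormalities without clinical significance based on the investigator's judgment, are not considered AEs or SAEs".
- **Protocol 7.3, reporting rule:** abnormalities that need intervention, come with signs or symptoms, or lead to IMP "interruption, modification, or discontinuation must be reported as an AE or SAE if they meet the definitions as described in Section 7.1".
- **Protocol 7.11.2** forbids dosing when a retest confirms platelets below LLN. For AST/ALT above 3 x ULN, bilirubin above 2 x ULN, ALP above 1.5 x ULN and deteriorating kidney function, it asks only that interruption or adjustment be considered with the medical monitor.

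**The concern.** Sections 7.2 and 7.3 do not say which governs when a laboratory value suggests an AESI but the subject is well. One site can report an asymptomatic low platelet count under 7.2, another can leave it out under 7.3, and both comply.

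The interruption route in 7.3 adds a structural difference between the parts. It needs an infusion that can be withheld. MAD has one nearly every time platelets are counted. SAD is a single dose, so its follow-up has none.

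At stake is the AESI part of the primary single-versus-multiple comparison. A higher platelet AESI frequency in MAD could reflect more complete recording rather than cumulative toxicity. The AESI table (14.3.1.2.6) is also marked for IDMC meetings 1 to 4, and the first two of those review SAD data before SAD2, SAD3 and MAD1 open.

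**Working it through.** **1. Reproduce the plan's own count.** Protocol Table 4 gives 31 local platelet samples per subject up to MAD Week 25. From the platelet rows of the Trial Schedules:

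- screening 1, baseline 1
- SAD follow-up 9 (Days 8, 15, 29, 43, 57, 71, 85, 99, 113)
- MAD 13 (Week 1 Days 1 and 4, Week 2 Day 8, Weeks 3 to 12)
- extension 7 (Weeks 13, 15, 17, 19, 21, 23, 25)

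1 + 1 + 9 + 13 + 7 = 31, as stated.

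**2. Counts at which a hold can trigger reporting.**

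- SAD follow-up: 0 of 9. No SAD infusion follows any of them.
- After the first MAD dose: (13 − 1) + 7 = 19 counts. All fall on a dosing visit except Week 1 Day 4, so 18 of 19. If no dose is given at Week 25, 17 of 19.

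The proviso in 7.3 about meeting the 7.1 definitions filters little, because 7.1 counts an abnormal laboratory finding as a possible AE.

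**3. Liver and kidney.** Section 7.11.2 has no mandatory hold for these below the trial stopping rule in 7.11.1 (confirmed, related ALT or AST above 8 x ULN). Whether a lesser asymptomatic value becomes an AE rests on judgement in SAD and in MAD. There is no built-in SAD/MAD difference.

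**4. What the laboratory tables show.**

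| Source | Shows | Does not show |
|---|---|---|
| SAP 6.14.2 shift tables | Below, within or above normal; worst result per trial period; local platelets included | Platelets below 75,000/µL; ALT/AST above 3 x ULN; bilirubin above 2 x ULN; ALP above 1.5 x ULN |
| Protocol 9.8 | Frequencies by CTCAE version 5 | Not carried into SAP 6.14.2 or the Section 12 output list |
| SAP 6.2.11 | Scheduled post-baseline values in tables | Repeat and unscheduled values, which are only listed |

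SAP 6.14.2 also uses the central result when both laboratories analysed the same sample, whereas the dose hold rests on the local result.

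**5. Illustration, platelets only.** These inputs are assumptions; the documents give no incidence. Let p be the true risk of a confirmed count below LLN, taken as equal in both parts, and q the share of asymptomatic falls judged clinically significant in SAD. Assume every such count is reported in MAD.

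- Gap in recorded incidence = p − pq = p(1 − q).
- With p = 0.30 and q = 0.75, 0.50, 0.25: 7.5, 15 and 22.5 points. With 6 subjects per dose level: 0.45, 0.90 and 1.35 subjects.
- Chance of at least one recorded event among 6 is 1 − (1 − pq)^6 in SAD and 1 − (1 − p)^6 in MAD. At q = 0.5:

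| p | Expected in SAD | Expected in MAD | Chance of ≥1, SAD | Chance of ≥1, MAD |
|---|---|---|---|---|
| 0.2 | 0.6 | 1.2 | 0.469 | 0.738 |
| 0.5 | 1.5 | 3.0 | 0.822 | 0.984 |

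With one criterion applied in both parts (q = 1) the gap is zero.

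**The case against.** The best defence is that the rules can be read together: 7.3 decides what is an AE, and 7.2 decides which AEs are flagged. Section 7.2 names conditions, and its sentence on laboratory signs asks for examination and retest. A reader might infer that 7.2 makes every abnormal value an AESI and that 7.3 flatly contradicts it. The text does not go that far. What remains is an ambiguity with no cut-off to settle it.

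A reader might also infer that reporting is forced throughout MAD. It is not. The point holds at most for confirmed low platelets at dosing visits, and even there the term interruption is undefined, so an infusion given slightly late within the ±3 day window might not count. Section 7.11.2 itself both bars dosing below LLN and says interruptions will be considered if related to IMP; those statements need reconciling. Nor is SAD pure judgement: symptoms, need for intervention and the stopping events in 7.11.1 force reporting there too.

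Next, the values are not lost. The shift tables show below-normal platelets by period whatever the AE decision, and they go to IDMC meetings 1 to 4. This stands, so the documents do not support a claim that a single-dose platelet signal would be hidden. It does not repair the AESI count, and it leaves the graded thresholds untabulated.

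Finally, the trial has no formal test, and SAP Section 8 says it was terminated and the planned primary analysis will not be run. New wording in 7.3 therefore has little prospective effect here. The added table still does: the full safety outputs are retained, and SAP Section 6 allows additional tables in the report.

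**Conclusion.** The concern holds in a limited form. For platelets, an asymptomatic confirmed fall meets a reporting trigger at 17 or 18 of 19 counts after the first MAD dose and at 0 of 9 in SAD follow-up, so the AESI part of the single-versus-multiple comparison is not like for like. For liver and kidney AESIs the count depends on judgement in both parts, which weakens comparability between sites but does not by itself favour either part.

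The visit counts come from the documents. The size of any distortion does not. The 7.5 to 22.5 point gap is a platelet-only illustration resting on an assumed 30% risk, an assumed 25% to 75% judgement rate, complete reporting in MAD, and equal true risk after one dose and after up to 24 weekly doses. The last assumption isolates the artefact and is not a prediction.

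**What to change.** 1. **Protocol 7.2, 7.3 and 7.11.2.** Reconcile them so that one AESI reporting criterion applies in both parts, whatever the judged clinical significance and whether or not an infusion is due. This concerns reporting only and changes no dosing rule. Section 7.11.2 uses both LLN and 150,000/µL for platelets, so the criterion must say which is meant where a laboratory's LLN differs.
2. **SAP 6.14.1/6.14.2.** Beside the eCRF-flagged AESIs, add one table of subjects with at least one result beyond each existing 7.11.2 threshold: platelets below LLN and below 75,000/µL, ALT/AST above 3 x ULN, bilirubin above 2 x ULN, ALP above 1.5 x ULN. For kidney function, where 7.11.2 has no number, use the CTCAE version 5 grade already named in protocol 9.8. Derive it from all laboratory data, including local platelet counts and retests, by dose and separately for SAD and MAD plus extension. State that this table departs from SAP 6.2.11 by using repeat values.

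The cost is a short protocol clarification and one table from data already collected. If the reporting criterion is applied prospectively, more mild laboratory AESIs will fall under the 24-hour reporting rule in 7.2.
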